# 23.3 Adverse Event Reporting Instructions

Investigators will promptly record all solicited or patient-reported AEs and SAEs on the Registry AE eCRF.

All SAEs, non-serious ARs, hypersensitivity reactions, pregnancies in patients receiving Vimizim, and all occurrences of spinal cord compression (whether Vimizim was administered or not) will be entered on the AE eCRF and submitted to BPV within 1 business day of learning of the event.

Relevant follow-up information will be entered into the EDC system on the AE eCRF and submitted to BPV as soon as it becomes available and/or upon request.

If the EDC system is not available, all SAEs, non-serious ARs, hypersensitivity reactions, pregnancies in patients receiving Vimizim, and all occurrences of spinal cord compression should be reported to BPV by completing the Registry AE/SAE form, and faxing or emailing the completed report to BPV within 1 business day of learning of the event. Fax or email the report to:

[figure not shown]
**BPV AE [contact]

**BPV email:** [contact]

If any questions arise regarding safety reporting, please contact BPV directly at:

**[contact]

Proprietary and Confidential

Page 72

Investigators are encouraged to contact the Registry medical monitor if deemed necessary to discuss patient safety. Contact information for the medical monitor is as follows:

Name: [name] Address: [name]

[name]

US

**[contact] **Email:** [contact]

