Long-term safety events occurring during MARS after index or registry entry (which ever occurs later), including hypersensitivity events, will be evaluated by summarising the incidences of AEs by System Organ Class, Preferred Term, relationship to Vimizim, and severity in the Safety Population. Exposure-adjusted incidence rates and event rates while on treatment will be included as part of long-term safety evaluation. All AE summaries will include only treatment-emergent adverse events (TEAEs) and SAEs reported during the study period (AEs that occur after the first Vimizim infusion). Analyses of AEs of hypersensitivity and anaphylaxis, and AEs temporally related to a Vimizim infusion will be summarised by System Organ Class, PT, and severity All AEs will be coded using the most recent version of Medical Dictionary for Regulatory Activities (MedDRA).

Total and neutralizing antibody status will be summarised over the follow-up period.

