# 22 MANAGEMENT AND REPORTING OF ADVERSE EVENTS/ADVERSE REACTIONS

# 22.1 Safety Parameters and Definitions

Investigators are requested to report the following AEs/ARs that are considered important for the evaluation of Vimizim safety and ongoing risk-benefit assessments. Report the following to the sponsor within 1 business day:

- All AEs, regardless of causality, occurring within 24 hours of Vimizim infusion (refer to the definition of a hypersensitivity reaction temporally-related to a Vimizim infusion below);
- All SAEs occurring in patients administered at least 1 dose of Vimizim, regardless of causal attribution (refer to SAE definition);
- All non-serious ARs to Vimizim (refer to AR definition);
- All occurrences of spinal cord compression in patients participating in the Registry or the Registry Substudies as SAEs, whether Vimizim was administered or not; and
- Any pregnancy that occurs in a patient administered Vimizim;
- Unusual Failure in Efficacy: a situation where Vimizim fails to produce the expected intended effect, which may result in an adverse outcome for the patient, including an exacerbation of the condition for which the product is being used.

Non-serious AEs, other than those occurring within 24 hours of Vimizim infusion, that are considered related to the underlying disease and unrelated to Vimizim administration by Investigators do not require reporting for this Registry or the Registry Substudies due to the profusion of expected AEs caused by MPS IVA. In addition, SAEs occurring in patients that have never received Vimizim do not require reporting for this Registry or the Registry Substudies, with the exception of spinal cord compression as stated above.

Stable chronic conditions that are present prior to Registry or Registry Substudy entry that do not worsen should be documented in the patient's medical record. A pre-existing condition should be assessed as an AE if the frequency, intensity, or the character of the condition worsens during participation in the Registry or Registry Substudies and meets one of the criteria above for safety reporting.

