# 23.2 Eliciting and Recording AEs/ARs

Investigators will seek information on reportable AEs and SAEs at each patient contact, and will promptly record solicited or patient-reported safety information on the Registry AE eCRF.

All reportable events will be entered on the AE eCRF and submitted to BPV within one business day of learning of the event to facilitate timely review by BioMarin and to meet regulatory reporting requirements. AEs and SAEs should also be recorded in the patient's medical record to facilitate source data verification.

Investigators should use correct medical terminology/concepts when recording safety parameters on the AE eCRF. Avoid colloquialisms and abbreviations. Only 1 medical concept should be recorded in the event field on the AE eCRF.

If known, a diagnosis should be recorded on the AE eCRF rather than individual signs and symptoms. However, if a constellation of signs and/or symptoms cannot be medically characterised as a single diagnosis or syndrome at the time of reporting, each individual event should be recorded on the AE eCRF. If a diagnosis is subsequently established, it should be reported as follow-up information.

AEs occurring secondary to other events should generally be identified by their primary cause. For example, if severe diarrhoea is known to have resulted in dehydration, it is sufficient to record diarrhoea as the event on the AE eCRF. However, medically significant AEs occurring secondary to an initiating event that are separated in time should be recorded as independent events on the AE eCRF. For example, if a severe gastrointestinal haemorrhage leads to renal failure, both events should be recorded separately on the AE eCRF.

Reportable events that occur and resolve between patient evaluation time points should be recorded again on the AE eCRF if they recur.

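### Section 23.3 tells sites to enter every adverse event on the AE eCRF, while Section 22.1, footnote o of Table 8.1.1.1 and Section 23.2 limit entry to reportable events

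*Protocol*

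**What the plan says.** **Section 22.1** gives a positive list of six reportable items. Two of them are "All AEs, regardless of causality, occurring within 24 hours of Vimizim infusion" and "All SAEs occurring in patients administered at least 1 dose of Vimizim, regardless of causal attribution". The others are non-serious adverse reactions (ARs) to Vimizim, spinal cord compression in any participant, pregnancy in a treated patient, and unusual failure in efficacy. The section then exempts non-serious AEs outside the 24-hour window "that are considered related to the underlying disease and unrelated to Vimizim administration by Investigators do not require reporting for this Registry". The reason given is how many such events the disease itself is expected to produce. SAEs in never-treated patients are also exempt, apart from spinal cord compression.

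**Footnote o of Table 8.1.1.1** states which events go into the Registry database. It names the same classes except unusual failure in efficacy.

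**Section 23.2** says "Investigators will seek information on reportable AEs and SAEs at each patient contact", and sends all reportable events to the AE eCRF and to the sponsor's pharmacovigilance department.

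**Section 23.3** begins "Investigators will promptly record all solicited or patient-reported AEs and SAEs on the Registry AE eCRF", with no limit to reportable events. Its next sentence gives a shorter list for entry and submission, and the list is repeated for use when the electronic system is down. Neither list contains unusual failure in efficacy.

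**Section 18.1.7, Objective 2**, summarises AEs in the Safety Population by System Organ Class, Preferred Term, relationship and severity, and adds: "Exposure-adjusted incidence rates and event rates while on treatment will be included as part of long-term safety evaluation".

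**The concern.** A site that takes the first sentence of Section 23.3 literally enters non-serious, unrelated events on any day. A site that works from Section 22.1 does not. The analysis in Section 18.1.7 states no filter beyond treatment emergence and the study period, so whatever was entered goes into the counts. Two sites with identical patients could then show different all-AE rates. The same holds for a change of practice at one site over calendar time.

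This is a collection matter and cannot simply be left to the analysis plan. An analysis plan can set aside events that were entered. It cannot recover events that some sites were told they need not enter. Long-term safety is part of Objective 2 of this post-authorisation safety study, and the AE analyses are repeated for patients under 5 years (Objective 5) and for the two substudies (Objective 7).

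**Working it through.** The protocol states no AE rate, so there is no figure to reproduce. The check is a comparison of rules, followed by an illustration under stated assumptions.

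**Step 1: the rules side by side.** Is the event class to be entered?

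| Event class | 22.1 | Footnote o | 23.2 | 23.3, first sentence | 23.3, lists |
|---|---|---|---|---|---|
| AE within 24 h of infusion | yes | yes | yes, via 22.1 | yes | yes, via the hypersensitivity definition |
| SAE, treated patient | yes | yes | yes, via 22.1 | yes | yes |
| Non-serious AR | yes | yes | yes, via 22.1 | yes | yes |
| Spinal cord compression, anyone | yes | yes | yes, via 22.1 | yes | yes |
| Pregnancy, treated patient | yes | yes | yes, via 22.1 | not addressed | yes |
| Unusual failure in efficacy | yes | **no** | yes, via 22.1 | not addressed | **no** |
| SAE, never treated (other than cord compression) | no | no | no | **yes** | **yes** |
| Non-serious, not an AR, more than 24 h after infusion | no | no | no | **yes** | no |

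The first row of the last column needs a note. The Section 23.3 lists name hypersensitivity reactions, but Section 22.1 defines a temporally related hypersensitivity reaction as any AE from the start of an infusion to one day after its end. The class is therefore nearly the same as AEs within 24 hours.

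**Step 2: which disagreements can change a planned rate.**
- SAEs in never-treated patients cannot. Section 18.1.5.1 restricts the Safety Population to patients given at least one dose at or after registry entry.
- Unusual failure in efficacy is an inconsistency between lists. No effect on a planned AE rate can be shown from the protocol.
- The last row can. Section 18.1.5.3 counts on-treatment time as infusion date plus 7 days, so events between 24 hours and 7 days after an infusion lie inside the exposure time of the on-treatment rates.

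**Step 3: illustration for non-serious, non-AR events.** Assume weekly infusions and an even spread of these events over the week. The 24-hour window holds 24/168 = 14.3% of them, or (4 + 24)/168 = 16.7% if a 4-hour infusion is counted. The first sentence of Section 23.3 would capture all of them, which is 168/24 = 7.0 times as many, or 168/28 = 6.0 times. Clustering near infusions would reduce this ratio.

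**Step 4: illustration for the all-AE rate.** Let q be the share of all AEs that are non-serious, not ARs and more than 24 hours after infusion. Patient-time is the same under both rules, so the ratio of the broad-rule rate to the narrow-rule rate is 1/(1 − q).

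| q (assumed) | 0.1 | 0.2 | 0.4 | 0.6 | 0.8 |
|---|---|---|---|---|---|
| Rate ratio | 1.11 | 1.25 | 1.67 | 2.5 | 5.0 |

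If only a fraction f of patient-time is at sites using the broad rule, the pooled ratio is 1 + f·q/(1 − q). With f = 0.5 (assumed) this is 1 + 0.5 × 0.25 = 1.125 for q = 0.2, and 1 + 0.5 × 1.5 = 1.75 for q = 0.6. The protocol gives neither q nor f.

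**The case against.** The strongest reply is that one loose sentence stands against a clear governing list. Section 23.1 ties the reporting period to the events described in Section 22. Section 20 requires AE/AR reporting as described in Section 22. Section 23.2 and the severity and causality subsections all speak of reportable events. The first sentence of Section 23.3 nearly repeats a clause of Section 23.2, and solicited events may simply mean those that Section 23.2 tells sites to seek. Sites are trained on AE reporting, visited about twice a year and called about twice a year. Nothing shows that any site follows the broad reading.

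Most of this stands as a limit on the point. The contradiction remains, because patient-reported events are not confined to what was solicited, and Section 23.3 is the section headed as the reporting instructions.

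A second reply is that Section 23.3 means record everything and expedite a subset. That would be a workable rule, but the document does not carry it. Footnote o is itself a database-entry rule and names restricted classes, and Section 23.2 limits what is sought to reportable events. If that rule was intended, those two places need correcting.

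Three stronger readings are tempting and not supported:
- A reader might infer three different rules in Sections 22.1, 23.2 and 23.3. Section 23.2 sets no rule of its own and defers to Section 22.1.
- A reader might infer a further rule from the exemption in Section 22.1, since a late non-serious event unrelated to both drug and disease is neither listed nor exempt. But the section treats its list as the test: a worsening pre-existing condition must also meet one of the listed criteria. The exemption is untidy wording.
- A reader might infer that safety signals in general cannot be interpreted. The classes captured under every section include SAEs in treated patients, ARs and events near infusion, and hypersensitivity, anaphylaxis and infusion-related events are also summarised separately. No comparison by site or country is planned in the protocol.

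**Conclusion.** The contradiction between the first sentence of Section 23.3 and the restricted rule in Section 22.1, footnote o and Section 23.2 is established from the text. So is the omission of unusual failure in efficacy from the Section 23.3 lists and footnote o.

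The consequence for rates is confined to non-serious events that are not ARs and occur more than 24 hours after infusion, and to the all-AE, unrelated-AE, System Organ Class and Preferred Term totals and exposure-adjusted rates that include them. Rates of SAEs in treated patients, non-serious ARs and AEs within 24 hours are the same under each section.

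The size cannot be computed from the protocol. The ratios above show only how it depends on an unknown share of events and an unknown mix of site practice. They are not evidence that recorded rates differ. The case for acting is that the affected totals have no single collection rule behind them and that the correction is cheap.

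**What to change.** Reconcile the passages to one collection rule.

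1. Limit the first sentence of Section 23.3 to events reportable under Section 22.1, for example. If recording all AEs and expediting a subset was intended, say so instead and change Section 22.1, footnote o and Section 23.2 to match.
2. Make both lists in Section 23.3 and the list in footnote o match the six items of Section 22.1, including unusual failure in efficacy.
3. Word the exemption in Section 22.1 as the complement of its list, so that no event is neither listed nor exempt.
4. For data already collected, present events outside the Section 22.1 classes separately from the pooled AE rates where recorded seriousness, causality and timing allow them to be identified. State where timing relative to infusion is unavailable.

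Step 4 may be only partly achievable. Section 18.1.5.3 refers to infusion dates and an enzyme replacement log. But Section 11.11 asks for treatment information at entry, at new prescription and at dose changes, and Section 18.1.1 says only that it may be recorded. No passage shows that the time of each infusion is captured.

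The cost is a wording amendment, a memo to sites, and some events moving from tables to listings.

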# 23.4 Type and Duration of Follow-up after AEs/SAEs

The investigator should follow all reported events until resolved or stabilized, or the patient is lost to follow up. Resolution is defined as a return to baseline status or stabilization of the condition with the expectation that it will remain chronic. Resolution of AEs and SAEs (with dates) should be documented on the AE eCRF and in the patient's medical record to facilitate source data verification.

For some reported events, BPV may follow up by telephone, fax, electronic mail, and/or a monitoring visit to obtain additional case details deemed necessary to evaluate reported safety information.

# 23.5 Reporting of Pharmacovigilance Data to Competent Authorities

BioMarin will monitor the safety data generated from the Registry and Registry Substudies and consider their implications for the risk-benefit balance of Vimizim. Any new information that may affect the risk-benefit balance of Vimizim will be communicated to competent authorities in countries where Vimizim is authorised and to relevant healthcare providers. Information affecting the risk-benefit balance of Vimizim may include that arising from an analysis of ARs or of aggregated data.

Serious and non-serious ARs will be reported to competent authorities as expedited safety reports and/or in periodic safety update reports in accordance with applicable regulations.

# 24 PLANS FOR DISSEMINATING AND COMMUNICATING STUDY RESULTS

BioMarin is required to provide reports regarding disease and patient treatment outcomes obtained from the Registry participants to the US FDA, and the European Medicines Agency on an annual basis, as well as other regulatory bodies as applicable.

BioMarin recognizes the importance of communicating medical study data and, therefore, encourages the publication of these data in reputable scientific journals and at seminars or conferences. The details of the processes of producing and reviewing reports, manuscripts, and presentations based on the data from this study will be described in the Clinical Trial Agreement between BioMarin and the Investigator/Institution. Consideration for authorship of all publications will be based on compliance with Recommendations for the Conduct, Reporting, Editing and Publication of Scholarly Work in Medical Journals of the International Committee of Medical Journal Editors (http://www.icmje.org/icmje-recommendations.pdf) and Good Publication Practice guidelines guidelines published in: (Graf, 2009), http://dx.doi.org/10.1136/bmj.b4330).

# 26 ANNEX 1. LIST OF STAND-ALONE DOCUMENTS

None

Page 77

### 27 ANNEX 2. ENCEPP CHECKLIST FOR STUDY PROTOCOLS

Study title:							
EU PAS Register® number: Study reference number (if applicable):							
Sect	tion 1: Milestones	Yes	No	N/A	Section Number		
1.1	Does the protocol specify timelines for  1.1.1 Start of data collection  1.1.2 End of data collection  1.1.3 Progress report(s)  1.1.4 Interim report(s)  1.1.5 Registration in the EU PAS Register®  1.1.6 Final report of study results.						
Comn	nents:						
Sect	tion 2: Research question	Yes	No	N/A	Section Number		
2.1	Does the formulation of the research question and objectives clearly explain:						
	2.1.1 Why the study is conducted? (e.g. to address an important public health concern, a risk identified in the risk management plan, an emerging safety issue)						
	2.1.2 The objective(s) of the study?						
	2.1.3 The target population? (i.e. population or subgroup to whom the study results are intended to						

Date from which information on the first study is first recorded in the study dataset or, in the case of secondary use of data, the date from which data extraction starts.

2.1.4 Which hypothesis(-es) is (are) to be

be generalised)

tested?

<sup>2 Date from which the analytical dataset is completely available.

Page 78

Version 6: 23 February 2021

Sect	tion 2: Research question	Yes	No	N/A	Section Number
	2.1.5 If applicable, that there is no a priori hypothesis?				
Comn	nents:				
Sect	tion 3: Study design	Yes	No	N/A	Section Number
3.1	Is the study design described? (e.g. cohort, case-control, cross-sectional, other design)				
3.2	Does the protocol specify whether the study is based on primary, secondary or combined data collection?				
3.3	Does the protocol specify measures of occurrence? (e.g., rate, risk, prevalence)				
3.4	Does the protocol specify measure(s) of association? (e.g. risk, odds ratio, excess risk, rate ratio, hazard ratio, risk/rate difference, number needed to harm (NNH))				
3.5	Does the protocol describe the approach for the collection and reporting of adverse events/adverse reactions? (e.g. adverse events that will not be collected in case of primary data collection)				
Comn	nents:				
Sect	tion 4: Source and study populations	Yes	No	N/A	Section Number
4.1	Is the source population described?				
4.2	Is the planned study population defined in terms of:				
	4.2.1 Study time period				
	4.2.2 Age and sex				
	4.2.3 Country of origin				
	4.2.4 Disease/indication				
	4.2.5 Duration of follow-up				
4.3	Does the protocol define how the study population will be sampled from the source population? (e.g. event or inclusion/exclusion criteria)				
Comn	nents:				

Morquio	A R	egistry	Study	(MARS)	Ì

	tion 5: Exposure definition and assurement	Yes	No	N/A	Section Number
5.1	Does the protocol describe how the study exposure is defined and measured? (e.g. operational details for defining and categorising exposure, measurement of dose and duration of drug exposure)				
5.2	Does the protocol address the validity of the exposure measurement? (e.g. precision, accuracy, use of validation sub-study)				
5.3	Is exposure categorised according to time windows?				
5.4	Is intensity of exposure addressed? (e.g. dose, duration)				
5.5	Is exposure categorised based on biological mechanism of action and taking into account the pharmacokinetics and pharmacodynamics of the drug?				
5.6	Is (are) (an) appropriate comparator(s) identified?				
Comr	nents:				
	tion 6: Outcome definition and assurement	Yes	No	N/A	Section Number
6.1	Does the protocol specify the primary and secondary (if applicable) outcome(s) to be investigated?				
6.2	Does the protocol describe how the outcomes are defined and measured?				
6.3	Does the protocol address the validity of				
	outcome measurement? (e.g. precision, accuracy, sensitivity, specificity, positive predictive value, use of validation sub-study)				
6.4	outcome measurement? (e.g. precision, accuracy, sensitivity, specificity, positive predictive value, use of				
	outcome measurement? (e.g. precision, accuracy, sensitivity, specificity, positive predictive value, use of validation sub-study)  Does the protocol describe specific outcomes relevant for Health Technology Assessment? (e.g. HRQoL, QALYs, DALYS, health care services utilisation, burden of disease or treatment, compliance,				

BIOM	1AR	
------	-----	--

Sect	ion 7: Bias	Yes	No	N/A	Section Number
7.1	Does the protocol address ways to measure confounding? (e.g. confounding by indication)				
7.2	Does the protocol address selection bias? (e.g. healthy user/adherer bias)				
7.3	Does the protocol address information bias? (e.g. misclassification of exposure and outcomes, time-related bias)				
Comm	nents:				
Sect	ion 8: Effect measure modification	Yes	No	N/A	Section Number
8.1	Does the protocol address effect modifiers? (e.g. collection of data on known effect modifiers, subgroup analyses, anticipated direction of effect)				
Comm	nents:				
Sect	ion 9: Data sources	Yes	No	N/A	Section Number
Sect 9.1	Does the protocol describe the data source(s) used in the study for the ascertainment of:	Yes	No	N/A	
	Does the protocol describe the data source(s) used in the study for the	Yes	No	N/A	
	Does the protocol describe the data source(s) used in the study for the ascertainment of:  9.1.1 Exposure? (e.g. pharmacy dispensing, general practice prescribing, claims data, self-report, face-to-		No	N/A	
	Does the protocol describe the data source(s) used in the study for the ascertainment of:  9.1.1 Exposure? (e.g. pharmacy dispensing, general practice prescribing, claims data, self-report, face-to-face interview)  9.1.2 Outcomes? (e.g. clinical records, laboratory markers or values, claims data, self-report, patient interview including scales and questionnaires, vital		No	N/A	
	Does the protocol describe the data source(s) used in the study for the ascertainment of:  9.1.1 Exposure? (e.g. pharmacy dispensing, general practice prescribing, claims data, self-report, face-to-face interview)  9.1.2 Outcomes? (e.g. clinical records, laboratory markers or values, claims data, self-report, patient interview including scales and questionnaires, vital statistics)		No	N/A	
9.1	Does the protocol describe the data source(s) used in the study for the ascertainment of:  9.1.1 Exposure? (e.g. pharmacy dispensing, general practice prescribing, claims data, self-report, face-to-face interview)  9.1.2 Outcomes? (e.g. clinical records, laboratory markers or values, claims data, self-report, patient interview including scales and questionnaires, vital statistics)  9.1.3 Covariates and other characteristics?  Does the protocol describe the information		No	N/A	
9.1	Does the protocol describe the data source(s) used in the study for the ascertainment of:  9.1.1 Exposure? (e.g. pharmacy dispensing, general practice prescribing, claims data, self-report, face-to-face interview)  9.1.2 Outcomes? (e.g. clinical records, laboratory markers or values, claims data, self-report, patient interview including scales and questionnaires, vital statistics)  9.1.3 Covariates and other characteristics?  Does the protocol describe the information available from the data source(s) on:  9.2.1 Exposure? (e.g. date of dispensing, drug quantity, dose, number of days of supply		No	N/A	
9.1	Does the protocol describe the data source(s) used in the study for the ascertainment of:  9.1.1 Exposure? (e.g. pharmacy dispensing, general practice prescribing, claims data, self-report, face-to-face interview)  9.1.2 Outcomes? (e.g. clinical records, laboratory markers or values, claims data, self-report, patient interview including scales and questionnaires, vital statistics)  9.1.3 Covariates and other characteristics?  Does the protocol describe the information available from the data source(s) on:  9.2.1 Exposure? (e.g. date of dispensing, drug quantity, dose, number of days of supply prescription, daily dosage, prescriber)  9.2.2 Outcomes? (e.g. date of occurrence, multiple		No	N/A	

Sect	ion 9: Data sources	Yes	No	N/A	Section Number
	9.3.1 Exposure? (e.g. WHO Drug Dictionary, Anatomical Therapeutic Chemical (ATC) Classification System)				
	9.3.2 Outcomes? (e.g. International Classification of Diseases (ICD), Medical Dictionary for Regulatory Activities (MedDRA))				
